2.2.7 Dose Reductions of IMP

The protocol has been amended to include guidance on dose adjustments during dose escalation and treatment as well as detail on the taper schedule.

2.3 Change to Inclusion Criteria: Age Range

The minimum age requirement for this trial has been lowered from 4 years to 2 years to better encompass the applicable pediatric age range (given that the mean age of Rett syndrome (RTT) diagnosis is 2.5 years)¹. Homogeneity of the patient population (i.e., inclusion of patients that are post-regression and stable) will be ensured by the existing inclusion criterion 'Patient must be post-regression (\geq 6 months since last loss of hand use or verbal language or gross motor regression)'.

Safety data used to support the evaluation of CBD-OS in patients with RTT covers the age range proposed. Safety data (up to and including the 120-day Safety Update) was submitted into NDA 210365 and approved by the FDA on 25 June 2018 for the use of CBD-OS (Epidiolex[®]) for the treatment of seizures associated with Lennox-Gastaut syndrome or Dravet syndrome in patients 2 years of age and older.

2.4 Change to the Symptom Diary

Following caregiver feedback, as part of diary content validation work, an item addressing the impact of seizures was added to the caregiver assessment of Rett symptoms (symptom diary).

2.5 Minor Corrections, Clarifications and Administrative Changes

- Blood sampling volume requirements and the specified minimum weight requirements for blood sampling (i.e., laboratory sampling [haematology and biochemistry (including coagulation) Visit 2 procedures have been updated to

emphasise that investigator and caregiver assessments at Visit 2 must be completed prior to administration of IMP.

- Text has been added to Section 9.1.1.8 of the protocol to note that Visit 10 is only required for those patients who do not participate in the OLE trial, taper the medication prior to entering the OLE, or withdraw from the trial early and taper IMP.
- Medidata Safety Gateway will be implemented for this trial and will allow SAE and pregnancy reporting via eCRF rather than fax reporting. Potential cases of drug-induced liver injury will now be reported via email rather than fax reporting.
- As a change to the GW investigator's brochure (IB) format, the development core safety information is no longer a separate source from the IB. Section 12.9 of the protocol has been updated to confirm that notification of safety information to investigators, regulatory authorities and IRB/IECs will be provided through 2 sources, the IB or Council for International Organizations of Medical Sciences (CIOMS) reports. The protocol has been amended to note that the Client Service Receipt Inventory (CSRI) will be completed via interview. Administrative updates have been made throughout for consistency (NB, in the interest of brevity, minor changes to grammar, punctuation or formatting are not captured in this amendment document).

## Document History

Version	Date	Author	Description
Final 1.0	02FEB2021	[REDACTED]	Initial Version
Final 2.0	30MAR2021	[REDACTED]	Update to add clarification on: 

- Derivation of treatment received

- Imputation of AE dates for time to onset/resolution calculation

- Exposure outputs to produce

- AE analysis based on resolution

- Classification of ALT/AST

- ECG triplicates analysis

## 1. Overview

This statistical analysis plan (SAP) describes the planned analysis and reporting for GW protocol number GWND18064 (A randomized, double-blind, placebo-controlled trial to investigate the efficacy and safety of cannabidiol oral solution (GWP42003-P; CBD-OS) in patients with Rett syndrome (RTT), dated 07 Jul 2020 version #4.1. Reference materials for this statistical plan include the protocol and the accompanying sample data collection documents. Operational aspects related to collection and timing of planned clinical assessments are not repeated in this SAP unless relevant to the planned analysis.

The study objectives listed below are according to latest Clinical Study Protocol. The concept of statistical analysis has been changed, no inferential analysis will be performed in the study, the statistical analysis will be purely descriptive. The reason for this, as described in Section 8.5, is that due to potential impact of the COVID-19 pandemic to patients and site personnel the Sponsor made the decision to discontinue the trial.

The structure and content of this SAP provides sufficient detail to meet the requirements identified by the Food and Drug Administration (FDA), European Medicines Agency (EMA), and International Conference on Harmonization (ICH) of Technical Requirements for Registration of Pharmaceuticals for Human Use: Guidance on Statistical Principles in Clinical Trials.

The planned analyses identified in this SAP may be included in clinical study reports (CSRs), regulatory submissions, or future manuscripts. Also, post-hoc exploratory analyses not necessarily identified in this SAP may be performed to further examine study data. Any post-hoc or unplanned, exploratory analysis performed will be clearly identified as such in the final CSR.

The statistical plan described hereafter is an *a priori* plan. It will be finalized prior to any unblinded inferential or descriptive analysis of data pertaining to study GWND18064.

## 2. Study Objectives and Endpoints

### 2.1 Study Objectives

#### 2.1.1 Primary Objective

The primary objective is to evaluate the efficacy of 15 mg/kg/day GWP42003-P, compared with placebo, at the end of 24 weeks' treatment in reducing symptom severity in patients with RTT using the Rett Syndrome Behaviour Questionnaire (RSBQ).

#### 2.1.2 Secondary Objectives

Key Secondary Objective:

- To evaluate the efficacy of 15 mg/kg/day GWP42003-P, compared with placebo, at the end of 24 weeks' treatment in reducing symptom severity in patients with RTT using the Clinical Global Impressions - Improvement (CGI-I).

Other Secondary Objectives:

- To evaluate the efficacy of 5 mg/kg/day GWP42003-P, compared with placebo in:
  - RSBQ
  - CGI-I
- To evaluate the effect of GWP42003-P, compared with placebo, in other measures of disease severity.
  - RSBQ subscales.
  - Clinical Global Impressions - Severity (CGI-S).
  - 9-items Motor Behavioral Assessment (MBA-9).
  - Children's Sleep Habits Questionnaire (CSHQ).
- To evaluate the safety of GWP42003-P, compared with placebo, in patients with RTT.

### **2.1.3 Exploratory Objectives**

Exploratory Objectives:

- To evaluate the effect of GWP42003-P on caregiver and patient quality of life (QoL).
  - 36-item Short Form [SF-36] and Child Health Questionnaire Parent Form 50 [CHQ-PF50], respectively.
- To evaluate the effect of GWP42003-P on health utilization.
  - Hospital Services Use Questionnaire.
- Caregiver assessment of Rett symptoms (symptom diary).
- To determine the plasma concentrations of cannabidiol (CBD) and its major metabolites with the aim of evaluating exposure versus efficacy and safety and collecting data for population pharmacokinetic (PK) analysis.
- To evaluate the effect of GWP42003-P on exploratory biomarkers.

## **2.2 Study Endpoints**

### **2.2.1 Efficacy Endpoints**

#### **2.2.1.1 Primary Efficacy Endpoint**

The primary efficacy endpoint is the RSBQ (total score) for the 15 mg/kg/day GWP42003-P dose level compared with placebo at the end of 24 weeks.

#### **2.2.1.2 Secondary Efficacy Endpoints**

##### **Key Secondary Endpoint:**

- CGI-I for the 15 mg/kg/day GWP42003-P dose level compared with placebo at the end of 24 weeks.

##### **Other Secondary Efficacy Endpoints:**

- To compare 5 mg/kg/day GWP42003-P with placebo using:
  - RSBQ (total score)
  - CGI-I

- To compare 15 mg/kg/day GWP42003-P and 5 mg/kg/day GWP42003-P with placebo using:
  - RSBQ subscales.
  - CGI-S.
  - MBA-9.
  - CSHQ.

#### **2.2.1.3      Exploratory Efficacy Endpoint(s)**

- To compare 15 mg/kg/day GWP42003-P and 5 mg/kg/day GWP42003-P with placebo for the following endpoints:
  - Caregiver QoL questionnaire (SF-36).
  - Patient QoL questionnaire (CHQ-PF50).
  - Hospital Services Use Questionnaire.
  - Caregiver assessment of Rett symptoms (symptom diary).
  - Blood levels of exploratory biomarkers.

#### **2.2.1.4      Other Exploratory Endpoint(s)**

- Plasma concentrations of CBD and its main metabolites.

### **2.2.2      Safety Endpoints**

The safety profile of GWP42003-P compared with placebo will be assessed by measuring:

- Adverse Events (AEs).
- Clinical laboratory parameters.
- Vital signs.
- Physical examination procedures.
- 12-lead electrocardiogram (ECG).
- Effects on menstruation cycles.
- Suicidality.
- Change in growth and development by measurement of height, weight, serum insulin-like growth factor-1 (IGF-1) levels and Tanner Staging (for patients aged  $\geq$  7 years, or earlier if clinically indicated by onset of menarche or other signs of precocious puberty).

### **3. Overall Study Design and Plan**

#### **3.1 Overall Design**

This multisite trial consists of a double-blind, randomized, placebo-controlled design which will compare the efficacy of GWP42003-P versus placebo over a 24-week treatment period.

Patients will be randomized to receive 5 mg/kg/day GWP42003-P, 15 mg/kg/day GWP42003-P or matching volumes of placebo in a 2:2:1:1 ratio.

Following screening, eligible patients will complete a 2 to 4-week baseline period (patients can be randomized as soon as they have completed at least 2 weeks of baseline and all eligibility criteria are confirmed [including review of all clinical laboratory results and, if applicable, confirmation of *MECP2* pathogenic genetic mutation]). All patients entering the trial will be stratified by severity, based on their Clinical Severity Scale (CSS) score (either a CSS score within the range of 10–22, or a CSS score within the range 23–36). Patients will be randomized and will commence the 24-week treatment period, including up to 2 weeks dose escalation. The treatment period ends at Visit 9 (Day 169), after which patients will commence a 10-day taper period followed by the 4-week follow-up period. The 10-day taper period and 4-week follow-up period may not be required for patients continuing CBD-OS treatment under a separate protocol.

If a patient permanently discontinues treatment at any point during the trial, the investigational medicinal product (IMP) should be gradually reduced over 10 days (unless inadvisable due to an AE). Patients and caregivers will be encouraged to remain in the trial and continue to complete trial assessments and visits as per protocol.

If a patient withdraws from the trial at any point during the trial, they will be required to attend a withdrawal visit, if applicable taper the IMP and attend the end of taper visit, and then complete the 4-week follow-up period.

#### **3.2 Sample Size and Power**

252 patients will be randomized to receive 1 of 2 dose levels of GWP42003-P (5 mg/kg/day or 15 mg/kg/day) or matching placebo (5 mg/kg/day dosing volumes or 15 mg/kg/day dosing volumes) on a 2:2:1:1 basis. The placebo data for the 2 dose groups will be pooled for analysis. Pooling of the placebo dose groups will be implemented for efficacy and safety analyses. For safety analysis, summaries by placebo dose will also be presented.

Assuming a common standard deviation of 9.38 and using a 2-sided test at a 0.05  $\alpha$ -level, a total sample size of 252 patients (84 patients per active dose group and 42 patients per placebo group) will provide 90% power to detect a mean difference of 5 points in change from baseline to Visit 9 in RSBQ (total score) between 15 mg/kg/day of GWP42003-P and placebo, allowing for 10% withdrawals.

#### **3.3 Study Population**

Female or male patients aged 2–18 years (inclusive), who weigh at least 10 kg may enter the trial. Patients must have a clinical diagnosis of RTT (typical or atypical), defined according to RettSearch Consortium criteria. Patients must have a confirmed pathogenic genetic mutation of the *MECP2* gene. Patients can be enrolled if they qualify for inclusion criteria and if they do not meet any exclusion criteria. For complete list of inclusion/exclusion criteria, please consult clinical study protocol.

### **3.4 Treatments Administered**

The administered treatment is GWP42003-P oral solution or placebo oral solution. Mode of administration: to be taken orally twice daily (morning and evening) using the syringe(s) provided, preferentially with food i.e., within 30 minutes after the end of a meal and in line with the patients' normal feeding schedule and dietary habits. The time of IMP administration in relation to food should be kept consistent throughout the trial. Patients will take their first dose of IMP in the clinic at the end of Visit 2 (Day 1) and caregivers will be instructed how to measure and administer the IMP to the patient.

Patients will escalate IMP to the target dose level for their dose group over a period of up to 2 weeks depending on the target dose (e.g., no titration is required to 5 mg/kg/day while titration to 15 mg/kg/day takes 2 weeks [weekly increments of 5 mg/kg/day]). Following escalation patients will remain at their assigned target dose level for the duration of the maintenance period of the trial.

### **3.5 Method of Assigning Subjects to Treatment Groups**

At the start of Visit 1 (screening), enrolled patients will be allocated a unique patient number. After completion of assessments and confirmation of eligibility at Visit 2, patients will be randomized to receive 5 mg/kg/day GWP42003-P, 15 mg/kg/day GWP42003-P or matching volumes of placebo in a 2:2:1:1 ratio. All patients entering the trial will be stratified by severity, based on their Clinical Severity Scale (CSS) score (either a CSS score within the range of 10–22, or a CSS score within the range 23–36). GW will provide all IMP in a packed and labeled state and the RTSM system will identify the pack number(s) to be dispensed to the patient at each relevant visit, according to the treatment assigned in the randomization schedule.

### **3.6 Blinding and Unblinding**

The identity of IMP assigned to patients will be held by the RTSM system. The principal investigator (PI) at each site, or his/her designee, is responsible for ensuring that information on how to access the RTSM system is available to the relevant staff in case of an emergency and unblinding is required. A patient's treatment assignment should only be unblinded when knowledge of the treatment is essential to make a decision on the medical management of the patient. Unblinding for any reason will be considered a protocol deviation.

### **3.7 Schedule of Assessments**

A detailed schedule of events for the study is provided in [Table 1](#) .

**Table 1 Schedule of assessments**

Visit Number	1	2	3 a	4 a	5	6	7	8	9 b,c	10 d	11 a
Day Number (Visit window)	-28 to -14*	1 (+3)	8 (± 3)	15 (± 3)	29 (± 3)	57 (± 3)	85 (± 3)	127 (± 3)	169 (± 3)	179 (+3)	207 (+3)
Informed consent and assent e	X										
Demographics	X										
Medical history	X										
CSS	X										
Eligibility check	X	X									
Genetic analysis of MECP2 (if unknown) f	X										
Randomization		X									
Concomitant medications	X	X	X	X	X	X	X	X	X	X	X
Adverse events	X	X	X	X	X	X	X	X	X	X	X
Menstruation question (where appropriate)		X							X		
Physical examination (including weight)	X				X		X		X		
Height	X								X		
ECG	X				X	X	X	X	X		
Vital signs	X	X			X	X	X	X	X	X	
Clinical laboratory blood sampling (hematology and biochemistry) g	X				X	X	X	X h	X		
Dipstick urinalysis (where possible)	X								X		
Visit Number	1	2	3 a	4 a	5	6	7	8	9 b,c	10 d	11 a
Day Number (Visit window)	-28 to -14*	1 (+3)	8 (± 3)	15 (± 3)	29 (± 3)	57 (± 3)	85 (± 3)	127 (± 3)	169 (± 3)	179 (+3)	207 (+3)
Urine/Serum THC screen i	X										
Serum pregnancy test (if appropriate)	X								X		
PK blood sampling (IMP)					X j,k,l	X j,k,l	X j,k,l		X j,k,l		

Biomarker blood sampling	X								X		
Caregiver completed questionnaire	RSBQ	X	X			X	X	X	X		
	CSHQ		X			X	X	X	X		
	Caregiver QoL questionnaire (SF-36)		X							X	
	Patient QoL questionnaire (CHQ-PF50)		X							X	
	Symptom diary n	X	X	X	X	X	X	X	X		
Time and date of last IMP dose					X	X	X		X		
MBA-9			X					X		X	
CGI-S			X			X	X	X	X	X	
CGI-I					X	X	X	X	X		
Visit Number	1	2	3 a	4 a	5	6	7	8	9 b,c	10 d	11 a
Day Number (Visit window)	-28 to -14*	1 (+6)	8 (± 3)	15 (± 3)	29 (± 3)	57 (± 3)	85 (± 3)	127 (± 3)	169 (± 3)	179 (+3)	207 (+3)
Hospital Services Use Questionnaire		X			X	X	X	X	X		
Tanner Staging (where appropriate)	X								X		
Suicidality assessment	X				X	X	X	X	X	X	
IMP dispensing o		X			X	X	X	X	X		
IMP collection and compliance review					X	X	X	X	X	X	
Dosing diary p		X	X	X	X	X	X	X	X	X	

\*Patients can be randomized as soon as they have completed at least 2 weeks of baseline and all eligibility criteria are confirmed (review of clinical laboratory results and, if applicable, genetic analysis)

- l The time of the patients' sample collection, time of latest IMP dose, time and type of meal consumed by the patient closest to the latest IMP dose will be recorded, as well as the time of latest concomitant medications. For patients weighing < 16 kg, no blood sample will be collected for biomarker analysis.
- m Completed weekly throughout the trial.
- n In cases where patients are not able to attend study visits due to special circumstances (e.g., COVID-19 pandemic), the investigator will discuss with the Sponsor potential mitigation approaches for IMP dispensing, secure delivery, and collection.
- o Completed daily throughout the trial.

## 4. Statistical Analysis and Reporting

Statistical analyses will be performed after the database is locked. Only after the database has been locked will the unblinded statistician make the treatment allocations available.

### 4.1 Introduction

Data processing, tabulation of descriptive statistics, calculation of inferential statistics, and graphical representations will be performed primarily using SAS (release 9.4 or higher). If the use of other software is warranted, the final statistical methodology report will detail what software was used for what purposes.

Continuous (quantitative) variable summaries will include the number of patients (n) with non-missing values, the number of missing values, mean, standard deviation (SD), median, minimum, and maximum, unless otherwise specified.

Categorical (qualitative) variable summaries will include the frequency and percentage of patients who are in the particular category for each possible value. In general, the denominator for the percentage calculation will be based upon the total number of patients in the study population for the treatment groups, unless otherwise specified.

The number of missing values will be calculated as difference between the total number of patients in the study population for the treatment group and the number of non-missing values.

The minimum and maximum will be reported with the same degree of precision (i.e. the same number of decimal places) as the observed data. Measures of location (mean and median) will be reported to 1 degree of precision more than the observed data and measures of spread (SD) will be reported to 2 degrees of precision more than the observed data.

Percentages will be presented to 1 decimal place, unless otherwise specified.

### 4.2 Interim Analysis, Data Review

#### 4.2.1 Interim analysis

No formal interim analysis will be conducted.

#### 4.2.2 Data review

No blinded data review meeting will take place. After database lock, the study will be unblinded and descriptive statistical outputs will be created using the unblinded data.

## 5. Analysis Populations

The following analysis sets will be used for the statistical analysis:

### Screened

- All patients screened.

## Randomized

- All patients randomized.

## Intent-to treat set (ITT)

- All patients who are randomized, receive at least 1 dose of IMP in the trial, and have baseline efficacy data will be included and analyzed according to their randomized treatment arm.
- The ITT set is the primary analysis set for all efficacy endpoints.

## Safety Analysis Set

- All patients who receive at least 1 dose of IMP in the trial will be included and analyzed according to the treatment received. Only patients for whom it has been confirmed that they did not take any IMP will be excluded from this safety analysis set. This analysis set will be used to report the safety data. Treatment received will be derived using the real kits dispensed (reported in database) as following:
  - If patient took only placebo, assign to placebo.
  - If patient took mostly placebo but one dose of 5 mg/kg/day (or 15 mg/kg/day) then assign to 5 mg/kg/day (or 15 mg/kg/day).
  - If patient was assigned to CBD and took CBD then assign them to the dose group they were meant to be assigned to.

Analysis sets will be identified prior to database lock and unblinding of the trial data.

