8 TREATMENT PROCEDURES

8.1 Investigational Medicinal Product Dosage, Administration and Schedule

The IMP will be presented as an oral solution containing 100 mg/mL GWP42003-P or only excipients (in the case of placebo). For details regarding IMP formulations, see [Section 5](#).

Patients will be assigned 1 of 2 dose levels of GWP42003-P or matching volumes of placebo on a 2:2:1:1 ratio (up to 84 patients per active group and 42 patients per placebo group).

The use of placebo in the current trial is deemed necessary to reduce bias when evaluating the efficacy and safety of the active treatment. All patients will be permitted to continue current therapies.

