13.3 Analysis Sets

The following analysis sets will be used for the statistical analysis:

Full Analysis Set

- All patients who are randomized, receive at least 1 dose of IMP in the trial, and have post-baseline efficacy data will be included and analyzed according to their randomized treatment arm.
- The full analysis set (FAS) is the primary analysis set for all efficacy endpoints.

Study Code: GWND18064

EudraCT Number: 2018-003370-27

Clinical Protocol 4.1, 07Jul2020 (duplicate synopsis removed)

Safety Analysis Set

- All patients who receive at least 1 dose of IMP in the trial will be included and analyzed according to the treatment received. Only patients for whom it has been confirmed that they did not take any IMP will be excluded from this safety analysis set. This analysis set will be used to report the safety data.

Per Protocol Analysis Set

If there are a sufficient number of significant protocol deviations in the trial, a per protocol (PP) analysis set may also be presented. The PP set is defined as:

- All patients that are a subset of the FAS who have completed the trial with no major protocol deviations deemed to compromise the assessment of efficacy. Major protocol deviations will be identified and fully defined prior to unblinding of the trial. The PP analyses will only be conducted on efficacy endpoints.

Analysis sets will be identified prior to the unblinding of the trial data.

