13.6.3.2 Adverse Events

Adverse events will be coded according to the Medical Dictionary for Regulatory Activities dictionary.

A treatment-emergent adverse event (TEAE) is one that started, or worsened in severity or seriousness, following the first dose of IMP.

Descriptive presentations of TEAEs will be given by preferred term and SOC for the safety analysis set. The number of patients reporting at least 1 TEAE will be provided.

The following summaries will be produced as a minimum:

- All-causality TEAEs.

Study Code: GWND18064

EudraCT Number: 2018-003370-27

Clinical Protocol 4.1, 07Jul2020 (duplicate synopsis removed)

- Treatment-related AEs.
- All-causality TEAEs by maximal severity.
- All-causality serious TEAEs.
- Treatment-related serious TEAEs.
- TEAEs reported as leading to permanent cessation of IMP.
- Fatal TEAEs.

In the presentation of safety data, data from the GWP42003-P dose groups will be presented separately and compared with placebo. This will allow the possibility to explore any effects of the dose of IMP on safety endpoints.

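### The safety-set rule keeps a patient given the other active dose in error under the intended dose, although the set is defined by treatment received

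*SAP*

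**What the plan says.** Protocol 13.3 defines the safety set as follows: "All patients who receive at least 1 dose of IMP in the trial will be included and analyzed according to the treatment received". SAP section 5 repeats that definition and adds how it is to be put into practice: "Treatment received will be derived using the real kits dispensed (reported in database) as following". Three rules follow.

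- Rule 1: "If patient took only placebo, assign to placebo".
- Rule 2: "If patient took mostly placebo but one dose of 5 mg/kg/day (or 15 mg/kg/day) then assign to 5 mg/kg/day (or 15 mg/kg/day").
- Rule 3: "If patient was assigned to CBD and took CBD then assign them to the dose group they were meant to be assigned to".

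The classification feeds every safety table. Protocol 13.6.3.2 states: "In the presentation of safety data, data from the GWP42003-P dose groups will be presented separately and compared with placebo", so that effects of dose on safety can be explored. SAP Table 2 (section 6.1.1) sets up the two active columns under a heading for actual treatment.

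On the product, protocol 8.1 says: "The IMP will be presented as an oral solution containing 100 mg/mL GWP42003-P or only excipients". Under protocol 8.1.2 the daily volume is calculated from body weight, and the caregiver receives a dosing schedule.

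**The concern.** For patients assigned to CBD who took CBD, rule 3 is assignment as randomised under the name of treatment received. It makes no distinction between a patient who followed the assigned schedule and one who was given the other active level by mistake. The second patient's adverse events, laboratory values and ECG findings would appear in the column of a dose not taken, and would be missing from the column of the dose taken.

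The separation of 5 from 15 mg/kg/day is the trial's dose-related safety information. SAP sections 1 and 8 drop all formal testing, so the descriptive tables by arm are what the trial will report. The planned exposure outputs in SAP 7.4 cover dosing days, diary days, days with doses not taken, dose adjustments and route of administration. They do not show mg/kg/day received, so they would not reveal a patient in the wrong column.

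**Working it through.** The plan states no figure to reproduce. The check is to apply the three rules to each combination of assigned arm and treatment taken, and compare the result with treatment received.

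| Assigned | Taken | Rule | Group under the SAP | Matches treatment received? |
|---|---|---|---|---|
| 5 mg/kg/day | 5 | 3 | 5 | Yes |
| 15 mg/kg/day | 15 | 3 | 15 | Yes |
| 5 mg/kg/day | 15, in error | 3 | 5 | No |
| 15 mg/kg/day | 5, in error | 3 | 15 | No |
| 5 or 15 mg/kg/day | placebo only | 1 | Placebo | Yes |
| Placebo | mostly placebo, one dose at 15 | 2 | 15 | Follows the level taken |

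The third and last rows show the inconsistency. One dose at 15 mg/kg/day moves a placebo patient to the 15 group, while a full course at 15 leaves a patient assigned to 5 in the 5 group. The rules also say nothing about a placebo patient who took more than one active dose.

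**Can kits identify the level?** The inputs are one active strength of 100 mg/mL (protocol 5.1 and 8.1) and target doses of 5 and 15 mg/kg/day. Volume = dose / strength:

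- 5 / 100 = 0.05 mL/kg/day
- 15 / 100 = 0.15 mL/kg/day
- Ratio: 0.15 / 0.05 = 3

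The liquid is the same and the volume differs threefold. A kit record therefore appears to show active or placebo, while the level depends on the schedule the caregiver was given.

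**Effect of one patient on an event rate.** Contribution = 1 / n, where n is the number in the column.

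- Planned size (protocol 13.1), n = 84: 1/84 = 1.2 percentage points
- Assumed n = 30: 1/30 = 3.3 percentage points
- Assumed n = 20: 1/20 = 5.0 percentage points

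The sizes 30 and 20 are illustrations. SAP 9.5 says the trial was discontinued, but the documents give no achieved arm sizes.

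**Is it resolved elsewhere?** The SAP's document history lists the derivation of treatment received among the points clarified in version 2.0, so these rules are the considered text. SAP 9.5 says only in general terms that the analyses differ from the protocol because the trial was stopped; it does not name this rule. No other section sends a patient given the other active level to the level received.

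**The case against.** The strongest defence is that rule 3 has a sensible purpose. Under protocol Table 8.1.2-1 every patient in the 15 mg/kg/day arm takes 5 and then 10 mg/kg/day in the first two weeks, and protocol 8.1.2 lets patients remain below target. A literal dose-taken rule could move such patients into the 5 mg/kg/day column, which would be worse. This stands, and any rewording must preserve it. It does not justify applying the rule to outright errors between arms.

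A second defence is that such errors are unlikely or would be seen. Packs are allocated centrally (protocol 7.1). Adherence is reviewed by telephone around Days 8 and 15. Returned product is checked against expected usage (protocol 8.4). Deviations and all collected data are listed (SAP 7.2 and 6.1.10). This also has force, with two limits: a usage check made against a wrongly issued schedule may find nothing amiss, and a listing shows the patient without moving them to the right column.

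Third, the statement about kits is an inference. Protocol 5.3.1 says the amount dispensed takes account of dose group and weight, and neither the pharmacy manual nor the kit data are available. The common strength supports the inference but does not prove it.

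Three stronger readings are tempting and are not supported. A reader might infer that everyone randomised to an active arm is analysed as randomised; rule 1 already sends those who took only placebo to placebo. A reader might infer that titrating or dose-reduced patients are misclassified; they are following the protocol within their arm. A reader might infer that the reported safety results are wrong; the documents report no such dosing error.

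**Conclusion.** The concern holds in a limited form. For a patient who was assigned to CBD, took CBD and was given the other active level in error, rule 3 contradicts the treatment-received definition in both documents and is out of line with rule 2. The stated data source, kits dispensed, appears unable to correct this.

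The size cannot be established from the documents and may be nil. Each affected patient counts for 1.2 percentage points in a column of the planned size, or 3.3 and 5.0 points under the assumed sizes of 30 and 20. No hypothesis test or decision rule depends on it; what is at stake is the accuracy of the dose-separated descriptive safety tables. The conclusion rests on reading rule 3 literally and on kits not being specific to dose level.

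**What to change.** Amend SAP section 5 as follows.

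1. Use kits dispensed to separate active from placebo only, unless kit records can be shown to identify the dose level.
2. Limit rule 3 to patients who followed their assigned schedule, stating that titration and dose reductions permitted by the protocol count as following it.
3. Classify a patient given the other active level in error by the level received, taken from the dosing schedule issued and the recorded protocol deviations. Use reconciliation of returned product against weight, and diary volumes where they exist, as support only. The diary cannot be the main source: under protocol 8.4 a volume is requested only when the caregiver says the schedule was not followed, so a patient who faithfully followed a wrong schedule has no volume recorded.
4. State a rule for mixed exposure, covering changes between active levels and placebo patients with more than one active dose.
5. List every patient whose received group differs from the randomised group.

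The cost is a few sentences, a small added derivation and a check of site schedule records, since the documents do not say that the schedule issued is held in the database. If no patient was given the wrong active level, points 2 and 3 leave the tables unchanged.
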